8.3. Efficacy Analysis

8.3.1. Definition of Efficacy Variable(s)

8.3.1.1. Primary Efficacy Assessment

The Essential Tremor Rating Assessment (TETRAS) Performance Subscale Part 4 upper limb tremor score will be assessed at each clinic visit as specified in the Schedule of Assessments ([Appendix A](#)).

For the Performance Subscale Part 4 upper limb tremor score, all 3 maneuvers in the upper limb assessments of Part 4 (Subscale Items 4a, 4b, and 4c) will be completed for both arms, first for the left arm and then for the right. The Part 4 subscale ordinally rates postural (limbs extended forward maneuver, wing-beating [elbows flexed] maneuver), and kinetic (finger-nose-finger maneuver) tremor on a 0 to 4 severity scale in 0.5-point increments, with higher scores indicating more severe tremor. The overall Performance Subscale Part 4 upper limb tremor score range for a given side (left or right) is 0 to 12, and for both sides combined is 0 to 24.

The primary efficacy assessment is the change from baseline compared to placebo in TETRAS Performance Subscale Part 4 upper limb tremor total score for both sides combined at Day 29 based on the Full Analysis Set.

8.3.1.2. Secondary Efficacy Assessments

The secondary efficacy assessments include the TETRAS Performance Subscale Part 4 upper limb tremor score at timepoints other than Day 29 (see Section 8.3.1.1), and the Kinesia ONE™ accelerometer score, TETRAS Scale ADL score, and TETRAS total performance score at all visits.

8.3.1.2.1. Kinesia ONE™ Accelerometer Score

Kinesia ONE™ is an ISO-certified wireless motion sensor worn distally on the index finger, which utilizes 3 orthogonal accelerometers and 3 orthogonal gyroscopes to monitor three-dimensional motion. Via the Kinesia ONE™ software application, measures of three-dimensional motion are converted to scores ranging from 0 to 4, per assessed maneuver on a given side; higher scores indicate greater tremor severity. Motion in both arms is captured.

For this study, the forward outstretched postural tremor, lateral “wing beating” postural tremor, and kinetic tremor will be measured for left, right, and both sides. The total score on a given side is the sum of the three individual scores for the side, thus the total score for a given side ranges from 0 to 12; the total score for both sides ranges from 0 to 24.

The secondary efficacy assessments include the change from baseline compared to placebo in Kinesia ONE accelerometer scores at all visits.

8.3.1.2.2. Essential Tremor Rating Assessment Scale

[figure not shown]
Three different components of TETRAS will be assessed in this study. The TETRAS ADL subscale, total performance score, and performance subscale part 4 upper limb tremor score will each be separately assessed at each clinic visit as specified in the Schedule of Assessments ([Appendix A](#)).

[figure not shown]
For details on the TETRAS performance subscale part 4 upper limb tremor score, see [Section 8.3.1.1](#).

[figure not shown]
The ADL subscale assesses how ET is impacting typical activities of daily living (ie, speech, eating, drinking, dressing, personal hygiene, writing, occupational impairment, social impact, and activities affected by upper limb tremor). It consists of 12 items that are each rated on a scale from 0 (normal activity) to 4 (severe abnormality). The overall ADL score range is 0 to 48.

[figure not shown]
The total performance score is based on overall rating of tremor amplitude in the voice, limbs, head, face, trunk, and also measures functional task capabilities, ie, handwriting, spirograph, and holding a pen over a dot. Each of these items is rated on a scale from 0 (no tremor) to 4 (severe tremor). Collectively, the performance items generate an overall performance score from 0 to 64.

[figure not shown]
The secondary efficacy assessments include the change from baseline compared to placebo in the TETRAS scale ADL score and TETRAS total performance score at all visits and the TETRAS performance subscale part 4 upper limb tremor score at all visits other than Day 29.

8.3.2. Visit Windows for Efficacy Analyses

The scheduled visits will not be windowed and will be used at nominal visit value for treatment period visits (Day 1, Day 8, Day 22 and Day 29). Post-treatment visits (Day 42), as well as the unscheduled, end-of-treatment (EOT), and early termination (ET) visits, will be mapped to a scheduled visit for analysis using the date of collection/assessment and Day 1, first dose date, as a basis to determine study day and then study day will be mapped to the intended visit according to the visit windows specified in the table below. The mapping will follow the visit window in [Table 2](#). In order to accommodate as much data as possible into analysis, these windows have been widened relative to protocol-specified operational windows to have no gap between them; these windows are used for analysis purposes only.

[Table 2](#) displays visit windows for efficacy analysis.

Table 2: Visit Windows for Efficacy Analysis

Scheduled Visit	Study Day of Expected Visit	Study Day Window for Visit
Screening	Day -1	Days -28- Day -1
Day 1 Predose	Day 1 Predose	Day 1 Predose
Day 8 (± 1 day)	8	Day 1 Postdose to Day 11
Day 15 (± 1 day)	15	Day 12 to 18
Day 22 (± 1 day)	22	Day 19 to 25
Day 29 (+1 day)	29	Day 26 to 30
Day 42 (± 1 day)	42	\geq Day 31

Once analysis visits are assigned based on the visit windows, all visits, including scheduled visits, unscheduled visits, and EOT/ET visits, will be eligible for being flagged as the “analyzed record” within the analysis visit window; a participant’s individual analysis visit window could potentially contain more than 1 visit. In the event of multiple visits falling within an analysis window or in case of a tie relative to number of days from the scheduled study day, the following rules will be used in sequence to determine the “analyzed record” for the analysis visit window:

- If data from the scheduled visit is available within treatment period, then the scheduled visit data will be used.
- If no data from the scheduled visit within treatment period is available, then the windowed visit data will be used.
- If more than one visit is in the same target day window, the data closest to the target day will be used.
 - If there is a tie with distance from visits to target day, the visit after the target day will be used.

The summary by visit will use the “analyzed records” only – at most one per participant. The data not flagged as the “analyzed record” will be included in listings. An unscheduled visit that does not fall under any analysis window (e.g. in case one is available after Day 45) will remain in the database and will be included in the listings.

For assessments scheduled only at Day 1, Day 29/EOT and Day 42/EOS, [REDACTED] the following visit windows are used.

[figure not shown]
Table 3: Visit Windows for Other Efficacy Analysis

Scheduled Visit	Study Day of Expected Visit	Study Day Window for Visit
Day 1	Day 1	Day 1
Day 29 (+1 day)	29	Day 2 to 30
Day 42 (± 1 day)	42	\geq Day 31

8.3.3. Analysis of Efficacy Variable(s)

The efficacy analysis uses the Full Analysis Set and presents data by randomized treatment, unless specified otherwise. The following efficacy endpoints will be summarized descriptively by randomized treatment at each scheduled time point:

- TETRAS performance subscale part 4 upper limb tremor scores (individual and total score by side and combined) – observed, change from baseline, percent change from baseline
- Kinesia ONE accelerometer scores – observed, change from baseline, percent change from baseline
- TETRAS performance total score – observed, change from baseline, percent change from baseline
- TETRAS ADL score - observed, change from baseline, percent change from baseline

The TETRAS performance subscale part 4 upper limb tremor change from baseline total score, TETRAS performance total score, TETRAS performance subscale Part 4/6/7/8 score, and TETRAS ADL score will also be presented by the following subgroups:

- Age group: <65, 65-80 years
- Sex: Male, Female
- Race: White, Black or African American, Other
- BMI (<18.5, 18.5-<25, 25-<30, ≥ 30 kg/m²)
- Age at essential tremor diagnoses (< 40 years, 40-60, >60 years)
- Age participant thinks essential tremor started (< 40 years, 40-60, >60 years)
- Years with essential tremor diagnosis (3-<6 years, 6-10 years, >10 years)
- Years since participant thinks essential tremor started (3-<6 years, 6-10 years, >10 years)
- Alcohol helps tremor: Yes (Intermediate, Worked Well), No (No, a little), NA
- Baseline TETRAS performance subscale part 4 upper limb tremor score (<12, ≥ 12)

8.3.3.1. Mixed Effects Model for Repeated Measures

8.3.3.1.1. Analysis of Primary Efficacy Variable

The estimand for the primary efficacy endpoints is defined as follows:

5. *There are two treatment regiments for participants to be evaluated: SAGE-324 or placebo.*
6. *The target population consists of participants age 18-80 years inclusive, with diagnosis of essential tremor of at least 3 years duration.*
7. *The outcome for the primary efficacy endpoint is mean change from baseline in clinic-based TETRAS performance subscale part 4 upper limb tremor score at Day 29.*
8. *The population-level summary measure is the difference in mean change from baseline in clinic-based TETRAS performance subscale part 4 upper limb tremor score of between the two groups (SAGE-324 and placebo).*

This will be analyzed using a mixed effects model for repeated measures (MMRM); the model will include treatment, baseline TETRAS performance subscale part 4 upper limb tremor score, assessment timepoint, and timepoint-by-treatment as explanatory variables. All

explanatory variables will be treated as fixed effects. All postbaseline clinic visits will be included in the model. The main comparison will be between SAGE-324 and placebo at the 29-day timepoint. Model-based point estimates (ie, least squares means, 95% confidence intervals, and p-values) will be reported where applicable. An unstructured covariance structure will be used to model the within-participant errors. The Kenward-Roger approximation will be used to estimate denominator degrees of freedom.

If there is a convergence issue with the unstructured covariance model, Toeplitz or Autoregressive (1) [AR(1)] covariance structure will be used, following this sequence until convergence is achieved. If the model still does not converge with AR(1) structure, no results will be reported. When the covariance structure is not unstructured, the sandwich estimator for the variance covariance matrix will be derived, using the EMPIRICAL option in the PROC MIXED statement in SAS.

For each model, the comparison of interest will be between SAGE-324 and matching placebo at Day 29 time point, with model-based point estimates (i.e., LS means), 95% confidence intervals, and p-values will be reported for all time points.

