13.5. Efficacy Analysis

The estimand for the primary efficacy analysis is the treatment difference between SAGE-324 and placebo in mean change from baseline in clinic-based TETRAS performance subscale part 4 upper limb tremor scores at Day 29 based on the Full Analysis Set. This will be analyzed using a mixed effects model for repeated measures (MMRM); the model will include treatment, baseline TETRAS performance subscale part 4 upper limb tremor score, assessment timepoint, and timepoint-by-treatment as explanatory variables. All explanatory variables will be treated as fixed effects. All postbaseline clinic visits will be included in the model. The main comparison will be between SAGE-324 and placebo at the 29-day timepoint. Model-based point estimates (ie, least squares means, 5% confidence intervals, and p-values) will be reported where applicable. An unstructured covariance structure will be used to model the within-subject errors. If there is a convergence issue with the unstructured covariance model, Toeplitz compound symmetry or Autoregressive (1) [AR(1)] covariance structure will be used, following this sequence until convergence is achieved. If the model still does not converge with AR(1) structure, no results will be reported. When the covariance structure is not UN, the sandwich estimator for the variance covariance matrix will be derived, using the EMPIRICAL option in the PROC MIXED statement in SAS.

Similar to those methods described above for the primary endpoint, an MMRM will be used for the analysis of the change from baseline in TETRAS total performance scores, Kinesia ONE accelerometer scores and TETRAS ADL scores.

Other efficacy analyses will be specified in the SAP. In general, data will be analyzed using appropriate descriptive statistics or prespecified statistical methods as applicable; participant listings will be provided for all efficacy data. Participants will be analyzed according to randomized treatment for the purpose of efficacy unless otherwise specified.

Sensitivity analyses will be described in the SAP.

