5.2. Sample Size and Power

The sample size of this study is based on the assumption of a 3 points difference in the change from baseline TETRAS performance subscale part 4 upper limb tremor score between SAGE-324 and placebo with a standard deviation of 3.5 points. Under these assumptions, a sample size of 25 evaluable participants per group would provide 85% power for detecting a placebo-adjusted treatment difference of 3 points in TETRAS performance subscale part 4 upper limb tremor score assuming a 2-sided test at an alpha level of 0.05. By including 2 treatment groups and using a 1:1 randomization, a total of 50 evaluable participants are required. Assuming a nonevaluability rate of 15%, approximately 60 participants will be randomized. Additional participants may be enrolled if the dropout rate is greater than 15%.

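### The primary MMRM's covariance fallback uses a sandwich variance with no small-sample correction or df method, and ends with no model result: low severity, cheap to fix

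*SAP*

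**What the plan says.** SAP 8.3.3.1.1 sets out a sequence.

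- **First choice.** "An unstructured covariance structure will be used to model the within-participant errors". The next sentence gives the df method: "The Kenward-Roger approximation will be used to estimate denominator degrees of freedom".
- **If that fit does not converge.** "Toeplitz or Autoregressive (1) [AR(1)] covariance structure will be used, following this sequence until convergence is achieved".
- **Variance for any structure other than unstructured.** "the sandwich estimator for the variance covariance matrix will be derived, using the EMPIRICAL option in the PROC MIXED statement in SAS".
- **Last step.** "If the model still does not converge with AR(1) structure, no results will be reported".

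No df method or small-sample correction is named for the Toeplitz and AR(1) fits, and no other model follows AR(1).

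The current protocol (Amendment 4) has the same sandwich step and the same last step, in the synopsis and in 13.5. It does not mention Kenward-Roger. Its list of structures also differs, since 13.5 reads "Toeplitz compound symmetry or Autoregressive (1) [AR(1)] covariance structure will be used, following this sequence until convergence is achieved" and the SAP has no compound symmetry.

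SAP 8.3.3.1.2 carries a similar MMRM to the secondary endpoints, including individual Kinesia ONE items by side. Appendix C lists subgroup MMRM tables (for example 14.2.1.7 and 14.2.2.6). SAP 8.3.3.1.5 names ten subgroup factors and merges a category only when it holds fewer than 5 patients.

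**The concern.** There are two weaknesses, both in stated rules.

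First, an optimiser failure at AR(1) would by rule withhold the primary model estimate, its confidence interval and its p-value. A Day 29 ANCOVA on treatment and baseline could still be computed from the same data.

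Second, an uncorrected sandwich variance tends to be too small when there are few participants, so intervals are too narrow and type I error exceeds 5%. The SAP names neither a correction nor a reference distribution for these fits. Whoever programs the analysis would have to choose after seeing that the planned model had failed, and that choice changes the p-value.

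**Working it through.** **1. The plan's own figure.** SAP 5.2 rests on the "assumption of a 3 points difference in the change" from baseline, SD 3.5, 25 evaluable per arm, two-sided alpha 0.05.

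- SE = 3.5 × √(2/25) = 0.990, and 3/0.990 = 3.03.
- Normal power = Φ(3.03 − 1.96) = Φ(1.07) = 85.8%; noncentral t gives 84.4%. The stated 85% is reproduced.
- 50/(1 − 0.15) = 58.8, so 59, or 60 as 30 per arm. The stated figure of about 60 is reproduced.

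The sample size is not in dispute. It fixes the planned size used below.

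**2. Size of each model.** "All postbaseline clinic visits will be included in the model": Days 8, 15, 22, 29 and, if counted, 42. With k visits, unstructured has k(k+1)/2 covariance parameters, Toeplitz k and AR(1) 2.

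- k = 5: 15, 5 and 2.
- k = 4: 10, 4 and 2.

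**3. What Kenward-Roger adjusts.** It inflates the model-based covariance of the fixed effects and derives its df from that matrix. The sandwich replaces that matrix, so the adjustment does not carry over. This follows from how the methods are built, not from software documentation.

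**4. Simulated type I error of the Day 29 treatment effect.** The design was 5 visits, the SAP's fixed effects, an AR(1) working covariance fitted by REML, and the uncorrected sandwich. Assumptions not in the documents are the true covariance (compound symmetry 0.6, AR(1) 0.75, or heterogeneous), dropout completely at random, a baseline slope of −0.3, and 15 per arm as the size of a smaller fit. Monte Carlo SE is about 0.2-0.4 points. The corrected column is a Mancl-DeRouen type sandwich with between-subject df.

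| True covariance | Per arm, dropout | Trials | z | Residual df | Between-subject df | Corrected | Sandwich SE / true SE |
|---|---|---|---|---|---|---|---|
| Compound symmetry | 25, 0% | 8,000 | 6.11% | 5.96% | 5.56% | 4.54% | 0.973 |
| Compound symmetry | 30, 15% | 8,000 | 6.11% | 6.05% | 5.55% | 4.56% | 0.967 |
| AR(1) | 25, 0% | 8,000 | 6.14% | 5.91% | 5.40% | 4.18% | 0.990 |
| AR(1) | 30, 15% | 4,000 | 5.85% | 5.78% | 5.35% | 4.45% | 0.997 |
| Heterogeneous | 30, 15% | 4,000 | 5.68% | 5.48% | 4.92% | 4.00% | 0.995 |
| Compound symmetry | 15, 15% | 8,000 | 7.54% | 7.27% | 6.26% | 4.07% | 0.949 |
| AR(1) | 15, 15% | 4,000 | 8.32% | 8.08% | 6.95% | 4.22% | 0.943 |
| Heterogeneous | 15, 15% | 4,000 | 7.35% | 7.07% | 5.95% | 4.08% | 0.950 |

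A separate simulation of the same kind (2,500-3,000 runs per scenario) at 5 per arm gave 14.1-14.7% with z, 13.1-13.4% with residual df and 8.4-9.0% with between-subject df.

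**5. Where fallback is realistic.** A subgroup category of 5 patients across both arms is kept. After arm-by-visit means, at most 5 − 2 = 3 between-subject df remain, too few for an unstructured 5 × 5 matrix. The site-exclusion sensitivity analysis (Appendix C, table 14.2.1.3.2) drops 13 sites of about 30 planned, so it too is a smaller fit.

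**6. Chance of reaching the last step.** None of 16,000 AR(1) fits checked failed or reached the boundary. The search was bounded and over one parameter, so this shows only that failure at AR(1) should be rare.

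**The case against.** The strongest reply is that this is nearly hypothetical for the primary analysis: three structures must fail in turn, the last with two parameters. That stands, and it is why the severity is low.

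Four stronger readings are tempting and are not supported.

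- **That the trial would report nothing.** SAP 8.3.3 separately plans observed values, change and percent change by arm at each time point, with no model. SAP 8.3.3.1.3 plans an imputation-based sensitivity analysis. What would be lost is the primary model result.
- **That Kenward-Roger and EMPIRICAL are conflicting rules.** Kenward-Roger directly follows the unstructured-covariance sentence, and the sandwich comes in the next paragraph, limited to other structures. Read in order, the defect is an omission in the fallback.
- **That the primary test is seriously inflated.** Simulations that extended dropout to 25% reached 6.7% with z. The plan's nonevaluability rate is 15%; 25% belongs to the superseded three-arm protocol.
- **That equal-variance, equal-lag structures are a separate defect**, since visits are 7, 7, 7 and 13 days apart. The sandwich is there to protect standard errors against a wrong working covariance. Heterogeneous Toeplitz or AR(1) would raise the parameter count from 5 and 2 to 9 and 6 in a convergence fallback, and would still ignore the unequal spacing. Pairing them with model-based Kenward-Roger would give up the robustness.

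It is also fair to say that withholding a non-converging subgroup estimate is defensible. The last-step rule therefore matters mainly for the primary, and the missing correction mainly for the small fits.

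**Conclusion.** The point holds as a cheap improvement, of low severity for the primary analysis.

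At the planned size the uncorrected sandwich costs at most about one percentage point of type I error (5.5-6.1% with z or residual df, 4.9-5.6% with between-subject df), and only if the unstructured model fails. At an assumed 15 per arm it is about 6-8%, and higher in very small subgroup categories, where that failure is realistic. Reaching the last step is unlikely, but it would remove the primary estimate and p-value.

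The last-step rule and the missing df method can be read directly from the text. The sizes rest on the assumed covariances and on dropout completely at random; dropout that depends on earlier scores was not examined.

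**What to change.** 1. Replace the last sentence of the SAP 8.3.3.1.1 fallback paragraph with: *If no structure converges, the Day 29 change from baseline will be analysed by ANCOVA with treatment and baseline score.* State its cost. It uses only participants with Day 29 data and discards the earlier visits of the rest, so it makes a stronger missing-data assumption than the MMRM. If all of the planned 15% lacked Day 29, that would be 0.15 × 60 = 9 participants.
2. For Toeplitz and AR(1) fits, specify a small-sample-corrected sandwich (for example Mancl-DeRouen type) with between-subject df, and say that Kenward-Roger applies to the unstructured fit only. In the simulations this gave 4.0-4.6% at the planned size and 4.1-4.2% at 15 per arm, slightly conservative. Name the procedure that computes it, since the present text gives only the EMPIRICAL option.
3. Make the same edit in protocol 13.5 and the synopsis, or state that the SAP supersedes them. Settle there whether compound symmetry is in the sequence.

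The cost is a few sentences and some programming before unblinding. No data, participants or sample size change.

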8.3.3.1.2. Analysis of Secondary Efficacy Variables

Similar to those methods described above for the primary endpoint, a MMRM will be used for the analysis of the change from baseline in other time points in TETRAS performance subscale part 4 upper limb tremor scores at all other visits/time points, TETRAS total performance scores, TETRAS ADL scores, and Kinesia ONE accelerometer scores, including total score and each individual item by side and combined total score. A MMRM will also be used for the analysis of the change from baseline in TETRAS performance subscale part 4 upper limb/part 6 (Archimedes spirals)/part 7(Handwriting)/part 8 (Dot approximation task) combined score.

Line plots of model-based LS Means and standard errors (SE) over time will be prepared for change from baseline in TETRAS performance subscale part 4 upper limb tremor total score (by side and combined), TETRAS performance total score, TETRAS performance subscale part 4/6/7/8 combined score, TETRAS ADL total score, and Kinesia ONE accelerometer total score (by side and combined).

[figure not shown]
